### 6.4. Clinical Laboratory Tests

The evaluation of clinical laboratory tests will focus on the following selected laboratory analytes:

- Hematology Panel:
  - hemoglobin
  - white blood cell (WBC) count, absolute neutrophil count, and absolute lymphocyte count
  - platelet count
- Serum Chemistry Panel:

- AST	- alkaline phosphatase
- ALT	- sodium
- total bilirubin	- blood urea nitrogen (BUN) or urea
- glucose	- serum calcium corrected for albumin
- creatinine	- potassium

Descriptive statistics for values and changes from baseline at each scheduled visit for hematology and chemistry laboratory parameters will be provided. Line plot of mean with standard error for each laboratory analyte over time will be displayed by treatment group for hemoglobin, neutrophils, lymphocytes, platelets, WBC, AST, ALT, creatinine, and creatinine clearance/GFR.

In addition, the worst toxicity grade in hematology and chemistry during the treatment will be summarized by treatment group and toxicity grade. Shifts tables from baseline to the worst toxicity grade during treatment will be generated.

A listing of subjects with any laboratory results outside the reference ranges will be provided.

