		Screening (within 35 days before randomization)	C1-2			C3-6		C7-39					
	standard of care within 56 days before randomization		D1 ^b	D8	D15	D22	D1	D15	D1	30 (±3) days after the last Daratumumab dose ^c	every 12 weeks (±7 days)	at least every 6 months (until end of study)	
Physical exam ^l	Symptom and disease directed exam as clinically indicated	X								X			
Height and weight		X											
Laboratory Assessments^e													
Pregnancy test (local laboratory) for women of childbearing potential		X (within 14 days before randomization)	as clinically indicated										
HBV serology ^k	Local testing for HBsAg, Anti-HBs, and Anti-HBc.	X	X (subjects ongoing in arm B only who are within 6 months of starting study treatment when Protocol Amendment 3 is implemented will be required to have HBV serology performed locally upon signing the updated ICF.)										
HBV DNA test	For subjects with serologic evidence of resolved HBV infection (ie, positive Anti-HBs or positive Anti-HBc) at Screening, HBV DNA testing by PCR must be performed locally.	X ^f	Q12W (for arm B patients, only) ^f						X (for arm B patients only) ^f	Q12W (for arm B patients only) ^f		Q12W (for arm B patients only) ^f	

	Notes	Active Monitoring (Arm A; 12-week disease evaluations) / Treatment Phase (Arm B; 4-week treatment cycles after Cycle 6) ^a (up to 39 cycles or 36 months, whichever occurs first)							End of Active Monitoring/ End of Treatment	Pre-PD Follow-up	PD	Post-PD Follow-up
		Screening (within 35 days before randomization)	C1-2			C3-6		C7-39	30 (±3) days after the last Daratumumab dose ^c	every 12 weeks (±7 days)		at least every 6 months (until end of study)
		D1 ^b	D8	D15	D22	D1	D15	D1				
Hematology Serum chemistry including calcium, albumin, creatinine SPEP, SIFE UPEP, UIFE Serum free light chain	Sample to be sent to local laboratory. After Cycle 1, IFE only when endogenous M-protein is 0 or nonquantifiable. Not required on C1D1 if screening values were obtained within 14 days of C1D1. In subjects with a baseline UPEP result below the level of measurable disease (<200 mg/24 hours), UPEP analysis will be repeated only at the time of suspected CR ^g	X	Every 12 weeks (window ±7 days)						X	X	Albumin only	
Quantitative immunoglobulin		X	yearly						X	yearly		
β2-microglobulin and lactate dehydrogenase	Sample to be sent to local laboratory	X									X	

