Notes		Treatment Phase (4-week treatment cycles up to 39 cycles or 36 months, whichever occurs first)									End of Treat- ment	8 weeks after last daratumu- mab dose		
		C1-2				C3-6			C7-C39					
		D1 ^a	D4	D8	D15	D22	D1	D4	D15	D1				
Refer to Site Investigational Product Procedures Manual for recommendations on daratumumab administration.														
Daratumumab ^g	SC injection over approximately 5 minutes. See Table 7 for acceptable window of administration.	X		X	X	X	X		X	X				
Pre- and Postdose Medications, see Section 6.3														
Other Study Procedures														
Hematology ^b (CBC with differential) (Local laboratory)	For C1D1, no need to repeat tests if they have been performed within the past 7 days. Testing may be performed up to 2 days before other administration days. Perform at additional timepoints, as clinically indicated.	Prior to every daratumumab administration: hemoglobin, white blood cell count with absolute neutrophils and lymphocytes, platelet count												
Chemistry (Local laboratory)		C2D1 and C3D1 (see Section 9.7 for specific laboratory tests)												
Blood group and type assessment and indirect antiglobulin test results ^c	To be obtained before start of administration; includes ABO, Rh, and indirect antiglobulin test results.	X												
Pharmacokinetic and Immunogenicity Assessments														
Pharmacokinetics ^d (send to central laboratory)		C1 (pre)	C1 ^e				C3 (pre), C5 (pre)	C3 ^f		C7 (pre), C12 (pre), C24 (pre)	X	X		
Immunogenicity Daratumumab ^{d,f} (send to central laboratory)	Use sample drawn for pharmacokinetics.	C1 (pre)					C3 (pre), C5 (pre)			C7 (pre), C12 (pre), C24 (pre)	X	X		

Notes		Treatment Phase (4-week treatment cycles up to 39 cycles or 36 months, whichever occurs first)									End of Treatment	8 weeks after last daratumumab dose
		C1-2					C3-6			C7-C39		
		D1 ^a	D4	D8	D15	D22	D1	D4	D15	D1		
Immunogenicity rHuPH20 ^{d,f} (send to central laboratory)	Draw dedicated sample after daratumumab pharmacokinetic sample is drawn.	C1 (pre)					C3 (pre), C5 (pre)			C7 (pre), C12 (pre), C24 (pre)	X	X

- a. C1D1 should occur within 5 days after randomization.
- b. Results of hematology tests must be evaluated before each daratumumab administration.
- c. A wallet card with the subject's blood type will be provided.

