9.7. Safety Evaluations

Details regarding the IDMC are provided in Section 11.12. Safety will be measured by adverse events, physical examinations, ECGs, SC injection-site evaluations, clinical laboratory test results (hematology and chemistry), and ECOG performance status. All toxicities will be graded according to the NCI-CTCAE Version 4.03. Any clinically relevant changes occurring during the study must be recorded on the Adverse Event section of the eCRF. Any clinically significant abnormalities persisting at the end of the study/early withdrawal will be followed by the investigator until resolution or until a clinically stable endpoint is reached.

Based on the previous human experience with daratumumab, in vitro studies, and animal toxicological findings, IRRs/allergic reactions, hemolysis, and thrombocytopenia will be closely monitored. As a biologic agent, immunogenicity also will be monitored. Any of the safety monitoring assessments may be performed more frequently, and adverse events should be evaluated by the investigator according to the standard practice, if clinically indicated.

The study will include the following evaluations of safety and tolerability according to the time points provided in the Time and Events.

Adverse Events

Adverse events (with the exception of progression to MM) will be reported by the subject (or, when appropriate, by a caregiver, surrogate, or the subject's legally designated representative) as specified in the Time and Events Schedule ([Table 1](#)). Adverse events will be followed by the investigator as specified in Section 12, Adverse Event Reporting.

Clinical Laboratory Tests

As per protocol Amendment 6, central laboratory assessments will be discontinued.

Local Laboratory Testing

For subjects in the daratumumab arm, blood samples for serum chemistry and hematology will be collected as outlined in the Time and Events Schedule and analyzed by the local laboratory before each dosing to determine if the subject meets daratumumab treatment criteria described in Section 6.5. The investigator must review the laboratory results, document this review, and record

any clinically relevant changes occurring during the study in the adverse event section of the eCRF. The laboratory reports must be filed with the source documents. Local laboratory data must be entered in the eCRF for safety evaluation.

The following tests will be performed by the local laboratory:

- Hematology Panel
 - hemoglobin

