11.10. Safety Analyses

Adverse Events

The verbatim terms used in the eCRF by investigators to identify adverse events will be coded using the Medical Dictionary for Regulatory Activities. Treatment-emergent adverse events are adverse events with onset during the active monitoring or treatment phase or that are a consequence of a pre-existing condition that has worsened since baseline. All reported adverse events will be included in the analysis. For each adverse event, the percentage of subjects who experience at least

1 occurrence of the given event will be summarized by treatment group. In addition, comparisons between treatment groups will be provided if appropriate.

Summaries, listings, datasets, or subject narratives may be provided, as appropriate, for those subjects who die, who discontinue treatment due to an adverse event, or who experience a severe or a serious adverse event.

Clinical Laboratory Tests

Laboratory data will be summarized by type of laboratory test. Reference ranges and markedly abnormal results (specified in the Statistical Analysis Plan) will be used in the summary of laboratory data. Descriptive statistics will be calculated for each laboratory analyte at baseline and for observed values and changes from baseline at each scheduled time point. Changes from baseline results will be presented in pre- versus posttreatment cross-tabulations (with classes for below, within, and above normal ranges). Parameters with predefined NCI-CTCAE toxicity grades will be summarized. Change from baseline to the worst adverse event grade experienced by the subject during the study will be provided as shift tables. A listing of subjects with any laboratory results outside the reference ranges will be provided. A listing of subjects with any markedly abnormal laboratory results will also be provided.

Electrocardiograms

Electrocardiogram data will be summarized based on categories of normal, abnormal either clinically significant or not clinically significant and listed.

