#### **Daratumumab 1800 mg SC (for daratumumab arm):**

- Cycles 1 and 2: Days 1, 8, 15, and 22 (QW)
- Cycle 3 to 6: Days 1 and 15 (Q2W)
- Cycles 7 to 39: Day 1 (Q4W)

Dose modification of daratumumab (increase or decrease) is not permitted. Dose delay is the primary method for managing daratumumab-related toxicities. Protocol-specified dose delays for daratumumab will be adjusted as necessary according to the treatment guidelines. Daratumumab may be delayed for up to 3 days, 7 days or 14 days during Cycles 1 and 2, Cycles 3 to 6 and Cycles 7+, respectively, to allow for recovery from toxicity. If daratumumab administration does not commence within the prespecified window of the scheduled administration date, then the dose will be considered a missed dose. A missed dose will not be made up. Doses of daratumumab in Cycles

7+ may be delayed up to 4 weeks. If a dose is delayed, then the dates of all subsequent doses must be adjusted. Any adverse event deemed to be related to daratumumab that requires a dose hold of more than 28 days will result in permanent discontinuation of daratumumab. Subjects missing 3 or more consecutive planned doses of daratumumab for reasons other than toxicity should be withdrawn from treatment, unless, upon consultation with the sponsor and the review of safety and efficacy, continuation is agreed upon. Subjects in daratumumab treatment group will be treated until disease progression, unacceptable toxicity, or other reasons as listed in Section 10.2 of protocol.

This study will use the IMWG consensus recommendations for MM treatment response criteria (Durie 2007, Rajkumar 2011, Kumar 2016). For quantitative immunoglobulin (QIg) at baseline, M-protein, and immunofixation measurements in serum and 24-hour urine, the investigator will use results provided by the central laboratory. Disease progression will be measured according to the published international uniform diagnostic criteria for MM established by the IMWG (Rajkumar 2014). Progression evaluations for the primary endpoint/final analysis will be based on IRC review, in a blinded fashion, to objectively and consistently implement the IMWG diagnostic criteria for MM.

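### SAP 6.4 tabulates worst hematology grade by arm although Arm B has about 3.8 times as many scheduled blood-count time points as Arm A, with no common-visit table and no stated laboratory source

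*SAP*

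**What the plan says.** SAP 6.4 (Clinical Laboratory Tests) plans that "the worst toxicity grade in hematology and chemistry during the treatment will be summarized by treatment group and toxicity grade", with shift tables from baseline to the worst grade. Protocol 11.10 plans the same kind of table: "Change from baseline to the worst adverse event grade experienced by the subject during the study will be provided as shift tables". Neither section mentions how often each arm is sampled.

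The sampling schedules differ. Protocol Table 1 puts hematology and chemistry every 12 weeks in both arms. Protocol Table 2, for Arm B only, adds local hematology: "Prior to every daratumumab administration: hemoglobin, white blood cell count with absolute neutrophils and lymphocytes, platelet count". It adds local chemistry only at Day 1 of Cycles 2 and 3. Protocol 9.7 says of the local results: "Local laboratory data must be entered in the eCRF for safety evaluation".

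SAP 6.4 does not say whether local or central results feed the worst-grade tables, and it does not define the treatment period for Arm A, which receives no treatment.

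**The concern.** A subject's worst grade is a maximum over that subject's readings, and a maximum tends to rise with the number of readings. When one arm is read several times as often as the other, the two columns differ even if the underlying counts behave identically. The effect is greatest for brief excursions, which a 12-weekly schedule can miss and a weekly one will usually catch.

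Cytopenia is a named potential risk of daratumumab in Protocol Table 3, and the comparator is an untreated, asymptomatic population. Readers will set the two columns side by side and tend to attribute the whole excess to the drug. The table cannot show how much of a difference is drug effect and how much is sampling.

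**Working it through.** The plan gives no figure for the number of readings, so the counts are built from the schedules.

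**Arm B pre-dose counts** (dosing schedule in SAP 1.2):
- Cycles 1 and 2, weekly: 2 × 4 = 8
- Cycles 3 to 6, every 2 weeks: 4 × 2 = 8
- Cycles 7 to 39, every 4 weeks: 33 × 1 = 33
- Total 8 + 8 + 33 = 49. Under SAP 2.6 the pre-dose reading on Cycle 1 Day 1 is baseline, which leaves 48 after baseline.

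**12-weekly visits, both arms** (Protocol Table 1; 36-month phase): 36 months is 156.5 weeks, and 156.5 / 12 gives 13 visits, at Weeks 12 to 156.

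**Overlap.** By SAP Table 2, Week 12 is Cycle 4 Day 1, Week 24 is Cycle 7 Day 1 and Week 36 is Cycle 10 Day 1. Continuing, 12 of the 13 visits (Weeks 12 to 144) fall on Arm B dosing days. Only Week 156 adds a new time point, so Arm B has 48 + 1 = 49 distinct post-baseline time points.

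**Ratio of distinct post-baseline time points:**

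| Up to week | Arm B | Arm A | Ratio |
|---|---|---|---|
| 24 | 16 | 2 | 8.0 |
| 52 | 23 | 4 | 5.8 |
| 104 | 36 | 8 | 4.5 |
| 156 | 49 | 13 | 3.8 |

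These are scheduled counts for a subject who completes 36 months. If sampling is assumed to stop at an exponential PFS event with the planned medians (30 and 48 months), the expected counts are about 40 and 8.6, a ratio of 4.6 to 4.7.

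**Chemistry** (Tables 1 and 2): 13 + 2 = 15 in Arm B against 13 in Arm A, or 1.15 to 1.

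**Illustration of the effect.** Assume the same chance p of a Grade 3 or higher value at every reading in both arms, with readings independent. The chance of at least one is 1 − (1 − p)^n, with n = 13 in Arm A and n = 49 in Arm B. The documents give no value of p, so a range is shown:

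| Assumed p | Arm A | Arm B |
|---|---|---|
| 0.2% | 2.6% | 9.3% |
| 0.5% | 6.3% | 21.8% |
| 1% | 12.2% | 38.9% |

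Serial counts in one person are positively correlated, which narrows the gap, so these figures are an upper bound on it.

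**Does another part of the plan correct this?** The by-week windows in SAP 2.1 are optional and serve over-time summaries. The preference for central results in SAP 4.1 is stated for the baseline laboratory summary. The time adjustment in SAP Attachment 1 covers adverse events only, and it adjusts for exposure time rather than sampling density. None reaches the worst-grade tables.

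**The case against.** The strongest reply is that SAP 6.4 never says the maximum is taken over all values. For baseline grades of the same panels, SAP 4.1 prefers central results, and SAP 1.2 has disease evaluations done centrally. If the worst-grade tables also used central results only, sampling would follow the common 12-weekly schedule and the problem would largely disappear. This stands as a limit on the claim: the bias is conditional on local values being used. But Protocol 9.7 enters local data for safety evaluation, and SAP 6.4 is silent on the source, so the condition is a live one.

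Second, the tables are descriptive, with no test planned. SAP 6.4 also gives values and changes by scheduled visit, and line plots by arm for hemoglobin, neutrophils, lymphocytes, platelets and white cells. Those do allow comparison at common visits. This stands too, and a claim that the benefit-risk judgement rests on the worst-grade tables would go too far. The by-visit summaries do not, however, give the proportion of subjects reaching a severe grade.

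Third, the bias runs against daratumumab, and a table confined to 12-weekly visits drops every post-baseline value before Week 12, a period that covers the first 10 doses. This is a sound reason not to replace the all-values tables. It is no reason against adding a second set.

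A reader might also infer a fivefold imbalance by adding the 49 pre-dose counts to the 13 visits (62 / 13 = 4.8). That counts the same days twice: two samples on one day are not two separate chances of finding a severe grade. Nor does the imbalance extend to all laboratory grades, since chemistry is nearly equal under the schedule tables. Protocol 9.7 can be read as requiring chemistry before each dose, but it defers to the Time and Events Schedule, which does not.

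**Conclusion.** The point holds for hematology, conditionally. Scheduled blood-count time points are 49 in Arm B and 13 in Arm A over 36 months (3.8 to 1), and 16 against 2 by Week 24 (8 to 1). If all recorded values enter the worst-grade and shift tables, the Arm B column is raised by sampling alone. The time-point counts follow from the schedules for subjects who complete the phase. The percentages rest on assumed per-reading rates and on independence, and show direction and an upper bound rather than a forecast.

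A reader might infer that any excess in Arm B would be a sampling artefact. The documents do not support that: a true drug effect on counts is plausible, and a persistent cytopenia would be found by 12-weekly sampling in either arm. What can be said is that the planned tables cannot separate the two sources.

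**What to change.** In SAP 6.4:

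1. Keep the all-values worst-grade and shift tables, with a note that hematology is scheduled about 3.8 times as often in Arm B over 36 months, and 8 times as often up to Week 24.
2. Add supplementary between-arm hematology worst-grade and shift tables limited to the common 12-weekly visits and the end-of-treatment or end-of-monitoring visit.
3. State for each table whether local or central results are used.
4. Replace the reference to the treatment period with the SAP 6.1 treatment-emergent window, which is defined for both arms.

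Separately, reconcile Protocol 9.7 and Protocol Table 2 on whether chemistry is drawn before each dose or only at the two listed time points. The near-balance for chemistry depends on the latter.

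The cost is a short SAP edit and one extra set of tables from data already collected. The common-visit tables will miss early transient nadirs; the retained all-values tables still show them.

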### 6.5. Vital Signs and Physical Examination Findings

Vital signs will be monitored as clinically necessary. Only abnormal vital signs and physical examination will be recorded in the eCRF, as part of AE reporting in the AE reporting page. No summary of vital signs and physical examination will be provided..

## 6.6. **Electrocardiogram**

The ECG data will be collected at Screening, visits as clinically indicated during treatment, and End-of-Treatment visit.

The number and percentage of subjects with normal and abnormal either clinically significant or not clinically significant ECG results will be summarized for each treatment group. A listing of subjects who experienced clinically significant abnormal ECGs in either baseline or post-baseline will be produced.

## 6.7. **ECOG Performance Status**

ECOG performance status, which evaluates the effect of the disease status on the activities of daily living, will be assessed at Screening, every 6 months during the treatment/active monitoring period, end-of-treatment/active monitoring visit and at PD. The shift summaries of ECOG performance status from baseline to each post baseline time points will be provided for each treatment group. The shift summary from baseline to the worst performance score during treatment/active monitoring will also be presented.

# 7. **PHARMACOKINETICS/PHARMACODYNAMICS**

## 7.1. **Pharmacokinetics**

All serum concentrations below the lowest quantifiable concentration or missing data will be labeled as such in the concentration data presentation. Concentrations below the lowest quantifiable concentration will be treated as zero in the summary statistics.

The pharmacokinetic parameters are defined as:

- $C_{\min}$  - Minimum observed concentration: defined as the concentration observed immediately before the injection
- $C_{\max}$  - Maximum observed concentration: defined as the first concentration observed after the end of the injection

The  $C_{\min}$ , and  $C_{\max}$  will be determined based on the assigned collection timepoints. If there are sufficient data, population pharmacokinetic analysis of serum concentration-time data of daratumumab may be performed using nonlinear mixed effects modeling and may include data from other clinical studies. If performed, details will be provided in a population pharmacokinetic analysis plan and results of the analysis will be presented in a separate report.

Descriptive statistics will be used to summarize daratumumab serum concentrations at each sampling time point specified in protocol. Plot of mean ( $\pm$ SD) daratumumab serum peak and trough concentrations over time will be provided.

If sufficient data are available, other pharmacokinetic parameters may be calculated and analyzed.

## 7.2. Immunogenicity

The incidence of anti-daratumumab antibodies along with the titer and incidence of neutralizing antibodies will be summarized for all subjects who receive at least 1 dose of Dara-SC and have appropriate samples for detection of antibodies to daratumumab (ie, subjects with at least 1 sample obtained after the first dose of daratumumab).

The incidence of anti-rHuPH20 antibodies along with the titer and incidence of neutralizing antibodies will be summarized for all subjects who receive a dose of Dara-SC and have appropriate samples for detection of antibodies to rHuPH20.

A listing of subjects who are positive for anti-daratumumab or anti-rHuPH20 antibodies will be provided.

